11.3. LOST TO FOLLOW-UP

Participants who do not show up for a scheduled non-intervention study visit will be contacted by available means (calling, email, text). If an emergency number is provided, it can be used to contact the participant, at least to ensure they are doing well. Participants who fail to respond to voice and written requests to contact the clinical site and who miss the Baseline Visit or 12-Week Visit will be considered lost to follow-up. Participants who miss their 24-Week Visit will not be considered lost to follow-up and will be sent the 36-Week timepoint questionnaires. A termination form should be completed by the investigator to record the exit of any participant deemed lost to follow-up.

12. STUDY ASSESSMENTS AND PROCEDURES

12.1. EFFICACY ASSESSMENTS

Study outcomes will be assessed by self-report using a series of validated instruments to measure pain intensity and interference, physical function, depression, anxiety, sleep disturbance and duration, and opioid use. Patient-reported outcome measures will be administered at study baseline as well as at 12-and 24-weeks following first-stage randomization using a web-based survey platform. The primary endpoint is based on the Pain, Enjoyment of Life, and General Activity (PEG) scale, a 3-item assessment of pain intensity and interference with enjoyment of life and general activity over the past week. Response values for each item range from 0 to 10 and the average score across the three items will be used as the outcome value.

Secondary outcome assessments include:

- PROMIS Pain interference scale (PROMIS-PI, 4a)
- Current use of opioid medication on a daily basis
- PROMIS Physical Function (PROMIS-PF Short Form 6b)
- PROMIS 4-item Depression scale (from the PROMIS 29 profile)
- PROMIS Emotional Distress-Anxiety scale (PROMIS-EDA 4a)

- PROMIS Sleep disturbance (PROMIS short form 6a)
- Sleep duration (reported number of minutes asleep per night over the past month)

Primary and secondary endpoints

- Primary endpoint: 24-week change from baseline in patient-reported pain intensity and interference, measured with the Pain, Enjoyment of Life, and General Activity (PEG) scale at Visits 0 (baseline) and 2 (24 weeks of treatment)
- **24-week change from baseline in pain interference**, measured with the 4-item PROMIS Pain Interference scale (PROMIS-PI, 4a) at Visits 0 (baseline) and 2 (24 weeks of treatment)
- Incidence of opioid use, measured by self-report at Visit 2 (24 weeks of treatment)
- **24-week change from baseline in physical function**, measured with the PROMIS-PF Short Form 6b at Visits 0 (baseline) and 2 (24 weeks of treatment)
- **24-week change from baseline in depression score**, measured with the PROMIS 4-item depression scale from the PROMIS 29 profile at Visits 0 (baseline) and 2 (24 weeks of treatment)
- **24-week change from baseline in anxiety score**, measured with the PROMIS Emotional Distress-Anxiety scale (PROMIS-EDA 4a) at Visits 0 (baseline) and 2 (24 weeks of treatment)
- **24-week change from baseline in sleep disturbance,** measured with the PROMIS short form 6a at Visits 0 (baseline) and 2 (24 weeks of treatment)
- **24-week change from baseline in sleep duration,** measured at Visits 0 (baseline) and 2 (24 weeks of treatment)

12.2. SAFETY ASSESSMENTS

Participants will be screened for contraindications to any of the BEST study interventions and phenotyping procedures prior to enrolling in the study. At the baseline visit, participant medical history will be obtained by the clinical coordinator and a physical assessment will be performed by a qualified medical professional. Basic safety assessments will be performed at 6 weeks (midpoint of intervention period one), 12 weeks (Visit 1), 18 weeks (midpoint of intervention period two), 24 weeks (Visit 2), and 36 weeks post-baseline (12 weeks after intervention period two) to assess participant tolerability to their current study intervention(s). Patients who are unable to tolerate their assigned study treatment will be educated on how to safely discontinue their current treatment plan but will otherwise remain in the study. Study staff will conduct an additional assessment of participants randomized to duloxetine via phone on day 7 (or next business day if falls on a weekend) of the intervention phase with participants newly randomized to duloxetine (i.e., day 7 of either the first or second intervention period).

Participants will be asked to report pregnancy status at multiple time points: prior to enrollment at Prescreening and Screening, and prior to randomization at the Baseline and 12-Week visits. Participants who report pregnancy prior to randomization to the first period intervention are excluded from the study. If the participant becomes pregnant during the study, duloxetine will be rapidly tapered. Participants who become pregnant during the study will not undergo study MRIs.

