Evidence-Based Exercise and Manual Therapy (EBEM): Manual therapy may be used to reduce pain and stiffness and improve range of motion, and exercises may be used to improve muscle strength, flexibility and endurance. Both are considered safe for the treatment of low-back pain, but side effects associated with spinal mobilization/manipulation and therapeutic exercise are common and benign. Approximately 50% of patients report local post-manipulation or exercise muscle and/or joint soreness which typically resolves within 24 hours. Participants may also receive soft-tissue mobilization, and risks associated with this procedure are considered to be mild. Mild muscle soreness at the site of soft-tissue treatment during and after treatment has been reported. Skin irritation has also been reported when massage lotions and oils were used. Exacerbation of any low-back problem is a common risk due to natural history of the condition. Education interventions may ask patients to discuss their pain experiences and the impact of their low back pain on various aspects of his or her life possibly resulting in emotional distress. EBEM is contraindicated for certain participants with uncontrolled high blood pressure or heart conditions.

Run-in: The Run-in period is comprised of informational materials delivered digitally. Risks are minimal.

Risks Associated with Confidential Information Disclosure

Despite significant protections being put in place to protect confidential participant information (e.g., protected health information (PHI)), breaches of confidentiality, while very unlikely, are possible. An example breach of confidentiality is the disclosure of a participant's protected health information to a party that is not approved to have access to that information. A breach of confidentiality will be considered as an unanticipated problem and, as such, will be reported to the IRB of record within 48 hours of the occurrence, and a remediation plan will be put in place immediately.

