otherwise eligible for the study will be allowed to participate in the study but will not be randomized to the intervention for which they have a contraindication. In Sections 10.1 (Acceptance Commitment Therapy), 10.2 (Duloxetine), 10.3 (Enhanced Self Care), and 10.4 (Evidence-Based Exercise and Manual Therapy) specific details regarding risk assessment and mitigation are given for each study intervention.

Participants will be advised that they should contact study staff regarding any side effects or unexpected adverse events that occur while enrolled in the study. Prior to the start of a new study intervention, participants will be informed that if they are unable to tolerate the intervention, they are permitted to cease the intervention. Specifically for duloxetine, participants will be instructed on how to safely taper off the medication. In addition, study staff will conduct a phone call assessment with all participants approximately midway into each of the two intervention periods to evaluate pain-related outcomes as well as to ascertain how well the participant is tolerating their current study intervention(s). Participants who indicate they are unable to tolerate the intervention will be safely transitioned off their current intervention but, if in intervention period one, will be allowed to be randomized to a new intervention in the second study period. Additionally, all participants will be assessed for unexpected and adverse events 4 weeks after the end of the second intervention period (i.e., after completion of all study treatment).

Acceptance Commitment Therapy: Participants will interact with their therapist at least weekly, and the therapist will provide support as well as monitor for worsening of depression or anxiety symptoms including suicidal ideation. Participants will be encouraged to contact study staff with questions or concerns throughout the course of the study.

Duloxetine: Participants on duloxetine will be monitored appropriately for clinical worsening, suicidality, or unusual changes in behavior. Participants may be referred for appropriate treatment including emergency services if required. Participation can also be discontinued if there is active suicidal ideation.

Enhanced Self Care: The ESC intervention is an educational and self-care digital intervention. Risks are minimal; therefore, no intervention-specific risk mitigation is planned.

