Participants randomized to the duloxetine arm will review the dosing schedule for the medication and safety information for the medication at the baseline visit with the study coordinator. At the baseline visit a physical assessment will be performed. Certain sections must be completed by a licensed medical professional (e.g., MD, DO, FNP, PA, PT). Drug contraindications (including allergy to duloxetine, concomitant antidepressant use, concomitant tramadol use, liver disease, kidney disease, concomitant of St. John's wort use) will be reviewed with the participant. Participants reporting a history of bipolar disorder, manic episodes, or suicide attempts will not be randomized to the duloxetine intervention arm. Participants will also be counseled on seeking emergency help if suicidal ideation occurs while on duloxetine.

Participants will be treated with duloxetine for 12 weeks during the active treatment phase. At the time of randomization, the approved drug pharmacy at each study site will dispense between 185 and 192 duloxetine 30 mg capsules and provide to participants. This will ensure enough to maintain up to a 60 mg dosage through the 12-week intervention phase and to taper the dose in through the 14th week if needed.

Duloxetine will be started at 30 mg, orally once per day in the morning for the first 7 days. Study staff will conduct an assessment via phone on day 7 (or next business day if falls on a weekend) of the intervention phase with participants newly randomized to duloxetine (i.e., day 7 of either the first or second intervention period). Study staff will document in the case response forms any adverse events and safety concerns the participants may have.

At the Day 7 assessment:

Participants tolerating the medication with no side effects (e.g. nausea) will be escalated to 60 mg (two 30 mg capsules) by mouth once per day in the morning.

Participants tolerating the medication with mild side effects will have the option to stay at 30 mg or discontinue the medication.

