Any medical condition that is present at the time that the participant is screened will be considered as baseline and not reported as an AE. However, if the study participant's condition deteriorates at any time during the study, it will be recorded as an AE.

Changes in the severity of an AE will be documented to allow an assessment of the duration of the event at each level of severity to be performed. AEs characterized as intermittent require documentation of onset and duration of each episode.

A site physician investigator or sub-investigator will record all reportable events between the time the participant provides informed consent through 4 weeks after their last treatment. At each study visit,

the investigator will inquire about the occurrence of AE/SAEs since the last visit. Events will be followed for outcome information until resolution, stabilization, or participant is off-study.

12.3.5.ADVERSE EVENT REPORTING

Serious Adverse Event Reporting

Study investigators will immediately notify the DAC of any serious adverse event, whether or not considered test treatment-related, including those listed in the protocol or investigator brochure. The report must include an assessment of whether there is a reasonable possibility that the treatment caused the event.

All serious adverse events (SAEs) will be followed until satisfactory resolution or until the site investigator deems the event to be chronic or the participant is stable. Other supporting documentation of the event may be requested by the DAC and should be provided as soon as possible.

- All AEs will be reported in aggregate to the NIAMS and the DSMB (through the NIAMS Executive Secretary) as part of the routine DSM report.
- All SAEs (regardless of relatedness or expectedness) will be reported to the NIAMS and the DSMB (through the NIAMS Executive Secretary) within 48 hours of the investigator becoming aware of the event.

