# Appendix 3 Table 3: Clinical Trials Adverse Event Reporting Table Other (Not Including Serious) Adverse Events Over a Threshold of 5%

Population: All Participants Randomized to Stage 1 (N=805); Including All Participants Randomized to Stage 2 (N=683)

	/ Threshold ing Other Events	5%							
System Organ Class	Preferred Term	Stage 1 ACT (N=xx)		Stage 1 Duloxetine (N=xx)		Stage 1 EBEM (N=xx)		Stage 1 ESC (N=xx)	
		Affected / at Risk (%)	# Events	Affected / at Risk (%)	# Events	Affected / at Risk (%)	# Events	Affected / at Risk (%)	# Events
	Total	x/N (x.x%)	у	x/N (x.x%)	У	x/N (x.x%)	У	x/N (x.x%)	
System Organ Class A	Preferred Term A1	x/N (x.x%)	у	x/N (x.x%)	у	x/N (x.x%)	У	x/N (x.x%)	У
System Organ Class A	Preferred Term A2	x/N (x.x%)	У	x/N (x.x%)	у	x/N (x.x%)	У	x/N (x.x%)	У
System Organ Class B	Preferred Term B1	x/N (x.x%)	У	x/N (x.x%)	У	x/N (x.x%)	У	x/N (x.x%)	У
System Organ Class B	Preferred Term B2	x/N (x.x%)	у	x/N (x.x%)	у	x/N (x.x%)	У	x/N (x.x%)	У

Othe	r (Not Inclu	ıding Serious)	Adverse E	vents					
Frequent Threshol Reportin Adverse	ld for g Other	5%							
	Preferred Term	Stage 2 ACT (N=xx)		Stage 2 Duloxetine (N=xx)		Stage 2 EBEM (N=xx)		Stage 2 ESC (N=xx)	
		Affected / at Risk (%)	# Events	Affected / at Risk (%)	# Events	Affected / at Risk (%)	# Events	Affected / at Risk (%)	# Events
	Total	x/N (x.x%)	у	x/N (x.x%)	у	x/N (x.x%)	У	x/N (x.x%)	
System Organ Class A	Preferred Term A1	x/N (x.x%)	У	x/N (x.x%)	у	x/N (x.x%)	У	x/N (x.x%)	у
System	Preferred Term A2	x/N (x.x%)	у	x/N (x.x%)	у	x/N (x.x%)	У	x/N (x.x%)	У
System Organ Class B	Preferred Term B1	x/N (x.x%)	у	x/N (x.x%)	У	x/N (x.x%)	у	x/N (x.x%)	У
System Organ Class B	Preferred Term B2	x/N (x.x%)	у	x/N (x.x%)	У	x/N (x.x%)	у	x/N (x.x%)	У

Othe	r (Not Inclu	ıding Serious)	Adverse E	vents					
Frequent Threshol Reportin Adverse	ld for g Other	5%							
	Preferred Term	Stage 2 ACT and Duloxetine (N=xx)		Stage 2 ACT and EBEM (N=xx)		Stage 2 ACT and ESC (N=xx)		Stage 2 Duloxetine and EBEM (N=xx)	
		Affected / at Risk (%)	# Events	Affected / at Risk (%)	# Events	Affected / at Risk (%)	# Events	Affected / at Risk (%)	# Events
	Total	x/N (x.x%)	у	x/N (x.x%)	У	x/N (x.x%)	У	x/N (x.x%)	
_	Preferred Term A1	x/N (x.x%)	У	x/N (x.x%)	У	x/N (x.x%)	У	x/N (x.x%)	у
System	Preferred Term A2	x/N (x.x%)	У	x/N (x.x%)	у	x/N (x.x%)	У	x/N (x.x%)	У
	Preferred Term B1	x/N (x.x%)	У	x/N (x.x%)	У	x/N (x.x%)	У	x/N (x.x%)	У
-	Preferred Term B2	x/N (x.x%)	у	x/N (x.x%)	У	x/N (x.x%)	у	x/N (x.x%)	У

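### First-week adverse events are solicited at Day 7 only in new duloxetine starters, and SAP Appendix 3 tabulates events by arm without separating them or saying so

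*Protocol*

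**What the plan says.** Protocol section 12.2 gives all arms one schedule: "Basic safety assessments will be performed at 6 weeks (midpoint of intervention period one), 12 weeks (Visit 1), 18 weeks", continuing to Weeks 24 and 36. Section 7.1 adds a safety assessment at Week 28. Section 12.3.4 sets the period covered by the question at each visit: "the investigator will inquire about the occurrence of AE/SAEs since the last visit".

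One contact is outside that schedule. Section 12.2 says "Study staff will conduct an additional assessment of participants randomized to duloxetine via phone on day 7" (or the next business day), for people newly randomized to duloxetine in either period. Section 10.2.1 makes it an adverse-event inquiry: "Study staff will document in the case response forms any adverse events and safety concerns the participants may have".

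SAP Appendix 3 reports deaths, serious events and other events in adjacent columns by Stage 1 arm and by Stage 2 treatment or combination, as number affected over number at risk with a percentage. Table 3 covers "Other (Not Including Serious) Adverse Events Over a Threshold of 5" per cent. Neither the SAP text nor the table shells mention the Day 7 call.

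**The concern.** A mild event that starts and ends in the first week is asked about within days on duloxetine. In the other arms the first scheduled question comes about five weeks after that, and the answer depends on memory. If the true rates were equal, the scheduled questions alone would find at least as many such events on duloxetine, and more whenever Week 6 recall is incomplete.

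Adverse events are one of the SAP's stated reporting aims, and percentages in adjacent columns will be compared. Without a note, a reader could take part of a difference in mild early events as a treatment effect when it reflects when the question was asked. Table 3 is the table exposed to this.

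**Working it through.** **1. Scheduled inquiries in Stage 1** (Protocol 10.2.1, 12.2, Appendix A)
- Duloxetine: Day 7, Week 6, Week 12 = 3.
- ACT, EBEM, ESC: Week 6, Week 12 = 2 each.

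In Stage 2 only new duloxetine starters get the Day 7 call. By Protocol Table 10.1 and the SAP columns, the Stage 2 duloxetine column can hold both people who switched to the drug and people who stayed on it. Each duloxetine combination column can likewise hold people who added the drug and people who added the other treatment to it.

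**2. Other routes to a report**
- All arms: participants are told to contact staff about side effects (5.2.3).
- ACT: at least weekly therapist interaction (5.2.3).
- EBEM: 10 face-to-face sessions, two a week in the first two weeks (10.4.1).
- ESC: no therapist (10.3).

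No adverse-event question is specified at the ACT or EBEM sessions, but events could be mentioned there.

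**3. Illustration of size.** The plan gives no figure to reproduce and no recall rate, so every input here is an assumption. Let p be the true risk of a transient first-week event, equal in all arms; c = 0.90 the capture at Day 7; r the recall at Week 6.
- Duloxetine shows p × [1 − (1 − c)(1 − r)].
- An arm with only the common schedule shows p × r.
- Gap = p × c × (1 − r), never negative, and zero at r = 1.

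For p = 8%, with the Stage 1 sizes in the SAP (duloxetine 198, ESC 205), the chance of exceeding 5% is the binomial probability of 10 or more of 198, or 11 or more of 205:

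| r | Duloxetine | ESC | Ratio | Chance over 5%: duloxetine | Chance over 5%: ESC |
|---|---|---|---|---|---|
| 0.3 | 7.4% | 2.4% | 3.10 | 0.93 | 0.01 |
| 0.5 | 7.6% | 4.0% | 1.90 | 0.94 | 0.20 |
| 0.7 | 7.8% | 5.6% | 1.39 | 0.95 | 0.60 |
| 0.9 | 7.9% | 7.2% | 1.10 | 0.96 | 0.88 |
| 1.0 | 8.0% | 8.0% | 1.00 | 0.96 | 0.94 |

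**4. Arms with clinician contact.** Let u be the share of first-week events that reach the record through sessions before Week 6. That arm then shows p × [1 − (1 − u)(1 − r)], and the gap becomes p × (1 − r) × (c − u). At p = 8% and r = 0.5:
- u = 0: 0.08 × 0.5 × 0.9 = 3.6 points.
- u = 0.5: 0.08 × 0.5 × 0.4 = 1.6 points.
- u = 0.9: 0.

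The documents do not give u, so the direction against ACT and EBEM is not settled.

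**5. EBEM soreness and the threshold.** Section 5.2.1 says: "Approximately 50% of patients report local post-manipulation or exercise muscle and/or joint soreness which typically resolves within 24 hours". At 30% recall, 0.50 × 0.30 = 15% would still be reported. Falling below 5% needs recall under 0.05 / 0.50 = 10%.

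**6. Restricting the table to events recorded at the common contacts.** Suppose an event already reported at Day 7 and resolved is not reported again. With p = 8%, c = 0.90 and r = 0.5, duloxetine would show 8% × 0.1 × 0.5 = 0.4%, against 8% × 0.5 = 4% in an arm with no other route. The bias would reverse.

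**The case against.** The strongest reply is that no between-arm safety comparison is planned. Protocol 13.4.4 limits safety analysis to descriptive summaries and listings, and the SAP excludes hypothesis testing. All arms are asked about the same period, anyone may report at any time, and closer watching of a drug is reasonable. All of this stands. It makes the issue one of how a descriptive table is read, and nothing here questions the monitoring. It does not answer the absence of any note in tables that place the arms side by side.

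A reader might infer more than the documents support, in three ways.
- **That duloxetine's relative harm is overstated against every other arm.** Steps 2 and 4 show that this is clear only for ESC.
- **That the 5% threshold would hide EBEM soreness, or hide an event in one column while showing it in another.** Step 5 rules out the first at any recall of 10% or more. On the second, the Table 3 shell gives each preferred term one row across the Stage 1 arms, and nothing says the threshold works column by column.
- **That suicidality or mood harm is undercounted in EBEM and ESC.** Section 5.2.3 says "Participants on duloxetine will be monitored appropriately for clinical worsening, suicidality, or unusual changes in behavior" and describes therapist monitoring in ACT. For ESC it says "Risks are minimal; therefore, no intervention-specific risk mitigation is planned", and for EBEM it mentions only soreness. But the duloxetine sentence specifies no added contact, instrument or record, so extra capture in the tables is conjecture. Mood is measured in every arm: Appendix A schedules the PHQ-2 and PROMIS 29+2 for all participants at Weeks 12 and 24.

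**Conclusion.** The point holds as a reporting weakness in SAP Appendix 3, chiefly Table 3. First-week adverse events are solicited on a schedule that one treatment has and the others lack, and the tables neither separate those events nor disclose the difference. Fuller capture of mild, transient first-week events on duloxetine is likely relative to ESC and uncertain relative to ACT and EBEM. Deaths and serious events should be little affected, because they are less likely to be forgotten by Week 6.

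The size is unknown. In the illustration the apparent ratio runs from 3.10 at 30% recall to 1.00 at full recall. That range rests on equal true risk, 90% capture at Day 7 and no other reporting route, none of which the documents state.

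**What to change.** Keep the Appendix 3 tables in full and add the following.

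1. A version of Table 3 that splits events in every arm by onset: within the first 7 days of the stage, or after day 7. Protocol 12.3.4 already requires time of onset for each event. The documents do not establish a separate Day 7 form, so onset is a safer basis than the contact at which the event was recorded.
2. Use the after-day-7 rows, which rest on the same scheduled inquiry in all arms, for reading across arms and for the 5% threshold.
3. A footnote that first-week events were solicited at Day 7 only in new duloxetine starters, and that Stage 2 duloxetine columns can mix new starters, who get the call, with continuers, who do not.
4. If suicidality is footnoted, say only that intervention-specific monitoring is described for duloxetine and ACT. PHQ-2 and PROMIS depression scores are available in all arms but measure mood, not suicidality.

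Do not use a table restricted to events recorded or still reported at the common contacts as the comparison between arms; step 6 shows how it would undercount duloxetine.

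The cost is SAP wording and one extra table, with no change to monitoring or data collection. The after-day-7 comparison leaves out true early duloxetine events, which the full table and the first-week rows still show. Onset dates recalled at Week 6 may be imprecise, so events with unclear onset should have their own row.

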Participants not tolerating the medication will be instructed to discontinue duloxetine. Participants in the first period intervention will be instructed to discontinue treatment until the next randomization point (Visit 1) at which time they will be randomized to a non-duloxetine second period intervention. Participants randomized to duloxetine in the second period intervention and not tolerating the medication will be instructed to discontinue duloxetine until their final follow-up of outcomes 24 weeks post baseline (Visit 2).

All participants will be provided with the site phone number and instructed to call if they have new or worsening side effects. If any safety or adverse events occur, the medication will be discontinued.

All participants will be assessed at the midpoint of the intervention treatment period (i.e., either Week 6 or Week 18) for tolerance, adverse events, and response. At the midpoint phone call:

Participants tolerating the medication with no side effects will be instructed to increase to 60mg/day (if currently taking 30mg/day) or remain on their current dosage (if currently taking 60mg/day).

Participants tolerating the medication with mild side effects (e.g. nausea) will be given the option of continuing their current dosage (30mg/day or 60mg/day), reducing their dosage (from 60mg/day to 30mg/day), or tapering off their current dosage (if currently taking 30mg/day).

Participants not tolerating the medication will be instructed to taper off the medication.

During the Week 18 call, participants will be reminded that their study treatment period is ending in six weeks. If they are tolerating the study medication and would like to continue duloxetine after the end of the treatment period, they should schedule an appointment with their provider to discuss continuing their duloxetine treatment outside of the study, in order to avoid a lapse in medication.

Tapering instructions:

The standard tapering period is up to two weeks. The following instructions will be provided to participants when they end their duloxetine treatment at either Visit 1 or Visit 2, or during the Week 6

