COVID previous diagnosis question	-				_	Х				-	\dashv			-	+	\dashv	\dashv		х	+	+	+	+	+	+	+	+	\dashv	-	_	H	Х	+	+	_	Х
Michigan Body Map		\vdash				Х				_	\dashv				+	-	\dashv		+		+	+	+	+	+	+	+		-				+	+	_	
PainDETECT	+	\vdash		\vdash	-	X		-	\vdash	\dashv	\dashv	\dashv	\vdash	\dashv	+	\dashv	\dashv	+	+	+	+	+	+	+	+	+	+		\dashv	_		\vdash	+	+	\dashv	
Patient Preference Tool		\vdash			_	Х				-	\dashv	\dashv			+	+	\dashv		Х		+	+	+	+	+	+	+	\dashv	-			Х	+	+	-	Х
Food Frequency Questionnaire	+	\vdash		\vdash	-	X		-	\vdash	\dashv	\dashv	\dashv	\vdash	+	+	\dashv	\dashv	+	+	\dagger	+	+	+	+	+	+	+		\dashv				+	+	\dashv	
Physical Assessment Randomization to 1st period Intervention	+	+		Н		X			Н	-	\dashv	Н	H	+	+	\dashv	\dashv		х	+	+	+	+	+	+	+	+		\dashv			Х		+	\dashv	
	+					X									+	\dashv	\dashv	+	х			+	+		+		+					x		+	\dashv	
Blood collection Stool collection	+			Н		Х	y*		Н		\dashv	Н	H	+	+	\dashv	\dashv	+	^	t	+	+	+	+	$^{+}$	+	+		\dashv			_		\dagger	\dashv	
Biomechanical assessment (light)	1						x*		Н			\exists	Н	\dashv	\forall	\dashv	\dashv	+	X x	*	+	+	+	$^{+}$	+	+	\forall					y	x*	+	\dashv	
Basic Spine MRI							x*								\top		\exists		1	Ī		\top	\top		T		1							T		
Activity monitoring (deep)	1	П					x*		П		\exists	\exists	П		\forall	\dashv	\dashv		\top	Ť	\dagger	\dagger	\dagger	†	Ť	+	1					T	T	Ť	\exists	
Biomechanical assessment (deep)		П					x*							\exists	\exists	\exists	\exists		X x	*	\top	\dagger	\top	T	Ť	Ť	\forall					х	x*			
Advanced Spine MRI	T											П		T	\dashv		\exists		Ť	Ī	\uparrow		1	T	T		1					Г	Τ	T	一	
Brain MRI						х	x*												х х	*												х	x*	*		
Quantitative Sensory Testing						х								J	Ī				х х				T	I	I								x*			
PGIC													х	J	Ī				х	Ι			T	I	I	х						х	\top	Ι		х
Intervention tolerance assessment/ Adverse Events													х		Ī		J		х	Ι			I	I		х						х		Ι		
End-of-study safety assessment																			I	I	I		I		I						Ĺ	Ĺ		\perp	х	
Randomization to 2nd period Intervention																			х															L		
Scheduling/Introduction/Onboarding to 2nd period Activities	1											ıΙ	ıĪ		- [х	1			- [- [1		"			1	- 1	

Schedule of Activities: The BEST Trial: Biomarkers for Evaluating, Spine Treatments (Pro00057948)***

Intervention-specific contact points				Fi	irst 1	treat	tmei	nt period	9	Second treatment period (maintenance subset)										
ACT intervention-specific contact points		х		х		х		х												

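### The only pregnancy question scheduled after Baseline is at Week 12, so for up to 12 weeks in each treatment period the duloxetine-taper and MRI rules rest on volunteered reports or general adverse-event inquiry

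*Protocol*

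**What the plan says.** Protocol Section 12.2 (Safety Assessments) gives the time points at which pregnancy status is asked: "prior to enrollment at Prescreening and Screening, and prior to randomization at the Baseline and 12-Week visits". It then sets two rules with no time limit within the study. On drug: "If the participant becomes pregnant during the study, duloxetine will be rapidly tapered". On imaging: "Participants who become pregnant during the study will not undergo study MRIs". Section 8.3 repeats the taper rule and Section 8.4 lists pregnancy as an imaging contraindication.

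Other contacts fall inside the treatment periods. On the day-7 call for those newly on duloxetine, Section 10.2.1 says: "Study staff will document in the case response forms any adverse events and safety concerns the participants may have". It describes the midpoint call as "i.e., either Week 6 or Week 18) for tolerance, adverse events, and response". Section 12.3.4 adds that at each study visit "the investigator will inquire about the occurrence of AE/SAEs since the last visit". The matching row of the Schedule of Activities (Appendix A) is labelled "Intervention tolerance assessment/ Adverse Events". None of these mentions pregnancy.

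For imaging, Section 5.2.3 describes a screening procedure for implanted materials and separately excludes participants who report pregnancy. Section 9.5 places brain MRI at Weeks 0, 12 and 24 for those in the optional phenotyping subset. The spine scans are at Baseline only.

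**The concern.** The taper and MRI rules apply throughout the study, but each works only once staff know of a pregnancy. After Baseline the listed schedule supplies one prompt, at Week 12. A site that follows Section 12.2 exactly could go through a whole duloxetine period without asking.

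The general safety inquiry is an imperfect substitute. Section 12.3.1 defines an adverse event as an untoward or unfavorable medical occurrence, and a participant with an uncomplicated pregnancy might not think to report it in answer to that inquiry. What is at stake is a delayed taper for someone who knows she is pregnant but has not been asked, and a Week 24 brain scan that relies on an old answer.

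**Working it through.** The plan states no figure on this point, so there is none to reproduce. The check sets the listed questions against the exposures they are meant to guard. All times are nominal weeks; visit windows are left to the Manual of Procedures.

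**Inputs**
- Pregnancy questions (Section 12.2): two before enrollment, then Week 0 and Week 12, each before randomization.
- Duloxetine treatment (Section 10.2.1): 12 weeks per period, so Weeks 0–12, Weeks 12–24, or both.
- Brain MRI in the optional subset (Section 9.5): Weeks 0, 12 and 24.
- Existing contacts during treatment (Sections 10.2.1 and 12.2, Appendix A): day 7 for those newly on duloxetine, then Weeks 6, 12, 18 and 24.

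**Step 1. Questions inside each period.** Strictly between Weeks 0 and 12: none. After Week 12 through Week 24: none. The Week 12 question sits on the boundary. It can reveal a pregnancy that began in period 1, but only once that period's 12 weeks are over.

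**Step 2. Longest interval on treatment without a question.**
- Period 1: 12 − 0 = 12 weeks.
- Period 2: 24 − 12 = 12 weeks.

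**Step 3. Age of the last scheduled answer at each brain MRI.**
- Week 0: 0 − 0 = 0 weeks.
- Week 12: 12 − 12 = 0 weeks.
- Week 24: 24 − 12 = 12 weeks.

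**Step 4. Do the other contacts fill the gap?** As described, they cover tolerance, adverse events, safety concerns and response. A participant could mention a pregnancy at any of them, but the text does not say that she is asked. I found no other scheduled pregnancy question and no pregnancy test in the readable Protocol, and the SAP adds none.

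**Step 5. After the fix.** With questions at Weeks 0, 6, 12 and 18, the intervals to the end of treatment are 6 − 0, 12 − 6, 18 − 12 and 24 − 18, each 6 weeks. A question at Visit 2 before the scan makes the age of the answer 24 − 24 = 0 weeks.

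**Step 6. Who is covered.** Stage 1 duloxetine is planned for 185 participants (Section 10.4.4); the SAP's baseline table shows 198. The number on duloxetine in Stage 2 is not given. For the Week 24 brain MRI, the Synopsis expects about 200 in the optional subset; if the 85% completion in Section 7.1 applies to them, 200 × 0.85 = 170. Section 9 instead expects about one third to opt in, and one third of the planned 630 completers is 630 / 3 = 210. These counts include all sexes. The documents do not give the share who could become pregnant, so no count of affected participants can be derived.

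**The case against.** The strongest reply is that the schedule is deliberate and adequate. The revision log for version 2.0 records that these time points were clarified and corrected. Pregnancy is asked before each randomization, which is when treatment is chosen. Section 11.2 names pregnancy on duloxetine as a safety risk that may justify discontinuation, the consent elements include risks to an embryo or fetus, and Section 5.2.3 tells participants to contact staff about side effects or unexpected events. No document sets a 6-week standard. The added question would also be self-report, so it could reveal only pregnancies that are known but not volunteered, and nothing in the documents says how many those are. Finally, the Manual of Procedures and site MRI forms are not available, and several rows of the Schedule of Activities run together in the available copy, so a check may exist there.

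Much of this stands. It limits the size of the point and makes the MRI part a request to confirm. It does not remove the mismatch between rules that apply all the time and a prompt that comes once after Baseline.

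Three stronger readings are tempting, and the documents do not support them:
- A reader might infer that no pregnancy question precedes the Week 24 MRI. All four precede it; the issue is that the latest is 12 weeks old.
- A reader might infer that a period-1 pregnancy would go unasked altogether. The Week 12 question covers it before re-randomization and at the visit of the Week 12 scan.
- A reader might run the Stage 2 gap on to the last permitted taper dose, 21 days after Visit 2: Week 27, or 27 − 12 = 15 weeks. By then the drug is already being withdrawn, which is the action a pregnancy would trigger, and Week 27 is reached only by a discretionary extension. That figure does not measure avoidable exposure.

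**Conclusion.** The point holds as a minor patient-safety improvement to the protocol text. Between the scheduled questions the taper rule depends on volunteered reports or general inquiry for up to 12 weeks in each duloxetine period, and the Week 24 brain MRI relies on an answer 12 weeks old unless a site form asks again.

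This rests on two assumptions: that Section 12.2 is the full list of scheduled pregnancy questions, and that the documents not available here add none. If they do add one, only a cross-reference is missing. Nothing here shows that a pregnancy was missed or that a pregnant participant would be scanned. The SAP already reports 805 participants randomized and 683 entering Stage 2, so the point concerns the protocol as written. The estimand, power and analysis are unaffected.

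**What to change.** Add the existing self-report pregnancy question to the Week 6 and Week 18 calls for participants on duloxetine, and at Visit 2 before any brain MRI. Because the Schedule of Activities allows the Week 24 scan on an optional second day, the question is best asked on the day of the scan. Update Section 12.2 and the Schedule of Activities to match. If the Manual of Procedures or the site MRI screening form already asks, cite it in Section 12.2 instead. The action on a positive answer stays as written.

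The cost is one extra question at contacts that already take place, with no new visit, test or staff.
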